8.2.2 Handling of Dropouts or Missing Data

We will perform a missing value analysis to check the volume of missing data and whether the missing data show patterns across subgroups. In case the missing values are non-ignorable, methods to correct for missing data will be used like, e.g., worst case scenario analysis, multiple imputation methods [Rubin 2004].

For the primary endpoint a worst-case analysis will be considered as a sensitivity analysis. For missing outcomes for the control group, the lower bound of the 95% confidence interval around the control mean will be imputed. For missing outcomes for the DCR group, the upper bound of the 95% confidence interval around the DCR mean will be imputed. The primary analysis will be repeated using the imputed values.

8.2.3 Efficacy Subset

As exploratory efficacy analyses subgroup analyses we will analyze the primary endpoint by 1, 2, 3 or more vessel PCI and by tertiles of the patients' SYNTAX score as approximation of the complexity of the PCI procedure.

8.3 Patient Disposition

Subject disposition, including the total number of subjects evaluated will be presented for the enrolled population. In addition, a listing will be provided with the reasons for why the subject was not evaluated.

For the randomized population the number and percentage of randomized subjects will be presented by site.

Document ID:	<As applicable, per local requirements>	Document title:	Classification:	For internal use
Modified:	11MAY2023	Statistical Analysis Plan	Author:	
Version:	3.0	Template ID: ClinicalStudyTemplate0025	Approver:	
Status:	Final	Template Version Date: 02MAR2018	Page:	25 of 52

Statistical Analysis Plan

A listing will present the randomized treatment for the randomized population.

A listing will present study population flags, study completion data, including the primary reason for study discontinuation for the enrolled population.

8.4 Demographics and Baseline Characteristics

Demographic and baseline variables will be summarized by treatment group for subjects in the Full Analysis Population (FAP). Age (years), height (cm), weight (kg) and body mass index (BMI) (kg/m^2) will be summarized as continuous data. Gender (Male/Female) and race (African American (Black), Non-African American, Unknown) will be summarized as categorical data.

We will perform statistical tests to compare the baseline characteristics of the two groups to check that the control and Dynamic Coronary Roadmap groups are similar at the start of the study. For categorical variables, we will perform a Chi-2 or Fisher Exact test, and for continuous variables a t-test or Wilcoxon-Mann-Whitney test as appropriate. When the groups are not comparable regarding baseline characteristics, adjustment for covariates will be applied as a sensitivity analysis (see section 8.14).

8.5 Medical History

Medical history will be summarized in categories by treatment group for subjects in the FAP and the SAF. A subject can have a medical condition in more than one category.

8.6 Medication use

Medication use will be summarized in categories by treatment group for subjects in the FAP and the SAF. A subject can have a medication use in more than one category. Also iodine contrast administration less than 1 week before the current PCI procedure will be summarized in this table.

8.7 Screening information

Left ventricular ejection fraction (LVEF) (%), systolic blood pressure (mmHg) and diastolic blood pressure (mmHg) at screening will be summarized for subjects in the FAP and the SAF.

Document ID:	<As applicable, per local requirements>	Document title:		Classification:	For internal use
		Statistical Analysis Plan			
Modified:	11MAY2023			Author:	
Version:	3.0	Template ID:	ClinicalStudyTemplate0025	Approver:	
Status:	Final	Template Version Date:	02MAR2018	Page:	26 of 52

Statistical Analysis Plan

8.8 Compliance

NA

8.9 Concomitant Therapy

NA

8.10 Procedure characteristics

Type of PCI (ad hoc PCI or elective (scheduled) PCI) and number of vessels treated by PCI (1 vessel PCI, 2 vessel PCI, 3 or more vessel PCI) will be summarized by treatment group for the FAP and the SAF. In addition, the SYNTAX score will be presented for the vessel(s) treated with PCI as an index for anatomical complexity. The SYNTAX score will be summarized in categories and as a continuous variable.

Also pre-procedural hydration (Y/N) and discontinuation of any renal drugs (e.g. ACE inhibitors) (Y/N) will be summarized in this table.

The access method (Transfemoral, Transradial, Other) and whether Femoral angiography was performed (if Transfemoral=Yes) and the timing of the Femoral angiography will be presented as categorical variables. Contrast usage details such as contrast injector (ml) at skin incision, generic name of iodine contrast used and contrast injector speed (ml/s) will be summarized.

The following information measured at the end of the PCI procedure will be summarized by treatment group for the FAP and the SAF:

- Procedure time (min)
- Total procedural contrast volume read-out of contrast injector (ml)
- Total number of stent(s) placed
- Total size of stent(s) placed (mm)
- Total number of balloon inflations
- Physiology assessment (instantaneous wave-Free Ratio (iFR) or Fractional Flow Reserve (FFR)) (Y/N)
- IVUS (Y/N)
- Any complication(s) during procedure (Y/N)
- Procedural success (Y/N)
- Total fluoroscopy time (mm)
- Total Air Kerma (mGy)

Document ID:	<As applicable, per local requirements>	Document title:		Classification:	For internal use
Modified:	11MAY2023	Statistical Analysis Plan		Author:	
Version:	3.0	Template ID:	ClinicalStudyTemplate0025	Approver:	
Status:	Final	Template Version Date:	02MAR2018	Page:	27 of 52

Statistical Analysis Plan

- Total Dose Area Product (DAP; Gy*cm²)
- Total Exposure DAP (Gy*cm²)
- Total Fluoroscopy DAP (Gy*cm²)
- Total number of exposure series (runs)
- Total number of exposure images
- Total number of contrast enhanced angiograms
- Total number of Stent Boost (runs)
- Post-procedural hydration (Y/N)
- Dynamic Coronary Roadmap used (Y/N)
- Overall quality and accuracy of roadmap (very good/ good/ fair/ poor/ very poor)

8.11 Efficacy Analysis

All efficacy outcomes will be presented for the Full Analysis Population and the Per Protocol Population.

8.11.1 Primary Efficacy Analysis

The primary endpoint of the study is the average total undiluted iodinated contrast volume (in ml) used per PCI (from first positioning the interventional guiding catheter in stable coronary position till end of PCI procedure) measured by an automatic contrast injector.

Hypothesis

Dynamic Coronary Roadmap reduces the total iodinated contrast volume used on average per PCI. The null and alternative hypotheses are as follows:

$$H_0: \mu_{\text{Control}} - \mu_{\text{DCR1}} \leq 0$$

$$H_a: \mu_{\text{Control}} - \mu_{\text{DCR1}} > 0$$

Where μ_{Control} is the average total iodinated contrast volume usage per PCI for the Control group, and μ_{DCR1} is the average total iodinated contrast volume usage per PCI for the DCR group.

Document ID:	<As applicable, per local requirements>	Document title:		Classification:	For internal use
		Statistical Analysis Plan			
Modified:	11MAY2023	Template ID:	ClinicalStudyTemplate0025	Author:	
Version:	3.0	Template Version Date:	02MAR2018	Approver:	
Status:	Final			Page:	28 of 52

Statistical Analysis Plan

Analysis

Descriptive summaries of the total undiluted iodinated contrast volume will be presented by treatment group for the FAP and the PP population and will include the number of subjects with non-missing data (n), mean with 95% confidence interval, standard deviation (SD), median, interquartile range (IQR) and minimum and maximum values.

The primary endpoint will be evaluated using a one-sided two-sample t-test. We will test for assumptions, e.g. normality and equal variances. Normality will be checked using histograms and Q-Q plots. If there are strong indications of non-normality, the data will be (log)transformed, and the back transformed results will be presented. Levene's test for equality of variances will be applied. When the p-value of this test is greater than 0.05, then we assume the variances are equal and we will use the arithmetic mean of the variances in calculating the standard error. When the p-value is less than or equal to 0.05, then we assume the variances are unequal and then we will calculate the standard error from the weighted average of the two variances.

All subjects in the full analysis population will be included in this analysis.

The results of the t-test will be displayed as estimates of the between treatment group difference (with 95% confidence intervals) and the (one-sided) p-value for the between treatment group difference. When the p-value is lower than the significance level of 2.5% (alpha) we will reject the null hypothesis.

The primary analysis will be repeated for the PP population.

In addition and for sensitivity purposes a worst-case analysis will be considered for the primary endpoint. For missing outcomes for the control group, the lower bound of the 95% confidence interval around the control mean will be imputed. For missing outcomes for the DCR group, the upper bound of the 95% confidence interval around the DCR mean will be imputed. The primary endpoint will be re-assessed with a complete dataset for the FAP population.

As a descriptive analysis, the (V) to creatinine clearance GFR ratio will be calculated. Assuming a contrast volume reduction by DCR, the contrast volume/GFR ratio will give information on how clinically meaningful this contrast reduction is. The ratio will be calculated by dividing the volume of contrast volume (in ml) received by the patients' GFR (in ml/min/1.73m²).

Document ID:	<As applicable, per local requirements>	Document title:		Classification:	For internal use
Modified:	11MAY2023	Statistical Analysis Plan		Author:	
Version:	3.0	Template ID:	ClinicalStudyTemplate0025	Approver:	
Status:	Final	Template Version Date:	02MAR2018	Page:	29 of 52

Statistical Analysis Plan

The CKD-EPI equation to estimate the glomerular filtration rate reads [Levey 2009]:

$$eGFR = 141 * \min(SCr/K, 1)^\alpha * \max(SCr/K, 1)^{-1.209} * 0.993^{Age} * 1.018 \text{ [if female]} * 1.159 \text{ [if black]}$$

with $K=0.7$ and $\alpha=-0.329$ if female

with $K=0.9$ and $\alpha=-0.411$ if male

Here min indicates the minimum of SCr/K or 1, and max indicates the maximum of SCr/K or 1. In case the race is unknown we will use 1 as multiplication factor.

As recommended by the ESC/EACTS Guidelines, the total contrast volume/GFR ratio should not exceed 3.7, because when the ratio is larger than 3.7 the risk for severe CKD ($eGFR < 30$) increases significantly [Laskey 2007, Neumann 2018].

The average V/GFR ratio (with 95% CI) and the proportion of patients with a V/GFR ratio > 3.7 (with 95% exact CI) will be presented by treatment group for the FAP.

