6.1. General

This is a multi-center, prospective, unblinded, stratified 1:1 randomized controlled trial to assess whether using Dynamic Coronary Roadmap reduces the total iodinated contrast volume related to PCI compared to the control group without Dynamic Coronary Roadmap. In the randomization process all subjects within each type of PCI (ad hoc or elective) will be stratified according to the number of vessels to be treated via PCI, i.e., 1, 2, or 3 or more vessel PCI.

A prospective multi-center study has been chosen to observe standard of care with the study device, see Figure 3 for the DCR4Contrast trial flow.

[figure not shown]

Figure 3 Clinical workflow of the DCR4Contrast trial following standard of care for PCI (ad hoc and elective)

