4.4.2 Randomization

The randomization will be performed via the Electronic Data Capture (EDC) system hosting the electronic Case Report Form.

In order to ensure balance of the treatment groups across subgroups, we stratified the randomization by site and within site by type of PCI (ad hoc or elective) and the number of vessels to be treated via PCI, i.e., 1, 2, or 3 or more vessel PCI. Within the subgroups we will perform a permuted block design. We will use a block size of 4 patients per block. There will be an equal allocation to the PCI procedure with DCR and the PCI procedure without the use of DCR (1:1 randomization).

In case of elective PCI, randomization will be done before the procedure and in case of ad hoc PCI randomization will be done upon decision to go for PCI right after diagnostics, so when the patient on the table still.

In enrolled subjects the investigator pre procedurally deemed no usage of OCT and/or the rotational or orbital atherectomy is required. During the PCI procedure usage of OCT and/or rotational or orbital atherectomy is left to the investigator's discretion.

In the case OCT and/or rotational or orbital atherectomy is used in enrolled subjects, these subjects will be replaced. When the decision is made to replace a subject this subject will not count for the required total number of subjects total, but will still be part of the Safety population. A new subject will be randomized to either of the arms.

Document ID:	<As applicable, per local requirements>	Document title:		Classification:	For internal use
		Statistical Analysis Plan			
Modified:	11MAY2023	Template ID:	ClinicalStudyTemplate0025	Author:	
Version:	3.0	Template Version Date:	02MAR2018	Approver:	
Status:	Final			Page:	11 of 52

Statistical Analysis Plan

Thus, the following subjects will be replaced:

- Subjects undergoing PCI supported by OCT will be replaced.
- Subjects undergoing PCI supported by rotational or orbital atherectomy will be replaced.

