4.5 Control to Minimize Bias

Ideally the study should be blinded, because there is potential intrinsic bias (sometimes referred to as the Hawthorne Effect) due to the fact the participants know that they are participating in a clinical study and know which arm they are participating in. However, as the Dynamic Coronary Roadmap is a visualization tool the study cannot be blinded.

Only standard guiding catheters will be used in the study and devices that could potentially confound contrast usage (e.g. rotational or orbital atherectomy device) will be excluded.

The methods to check whether the PCI was successful can include angiography, Stent Boost, and/or IntraVascular UltraSound (IVUS). Some of these procedures can include contrast agent volume, whereas others specifically do not (e.g., Stent Boost is a software feature). Therefore, the choice for checking the PCI result could introduce a bias based on individual users' preferences. Some PCI check methods are potential confounders for contrast usage and we will investigate to take measures to reduce the risk of bias based on site differences and user preferences. During site initiation it has been communicated that the PCI check procedure is to be standardized in both arms, which is standard of practice. This will be checked via remote monitoring of the eCRFs.

Analyses to determine whether there is an effect based on e.g. intervention difficulty (measured by the SYNTAX score), lesion characteristics, patient demographics, physician experience, center effect etc. will be performed. If an effect is found applying adjustment analysis, i.e. analysis of covariance adjusting for relevant confounders will be considered as a sensitivity analysis.

Document ID:	<As applicable, per local requirements>	Document title:	Classification:	For internal use
Modified:	11MAY2023	Statistical Analysis Plan		
Version:	3.0	Template ID:	ClinicalStudyTemplate0025	Approver:
Status:	Final	Template Version Date:	02MAR2018	Page: 12 of 52

Statistical Analysis Plan

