8.11.2 Secondary Efficacy Analysis

The secondary endpoint is the average total number of contrast enhanced cine angiographic X-ray runs (angiograms) per PCI (from first positioning the interventional guiding catheter in stable coronary position till end of PCI procedure) determined via visual assessment (e.g., on the Philips X-ray system To assess the total number of contrast enhanced cine angiographic X-ray runs (angiograms) related to PCI in the Dynamic Coronary Roadmap and control group

Hypothesis

Dynamic Coronary Roadmap reduces the total number of contrast enhanced cine angiographic X-ray runs (angiograms) acquired on average per PCI. The null and alternative hypotheses are as follows:

$$H_0: Pop_{Control2} \leq Pop_{DCR2}$$

$$H_a: Pop_{Control2} > Pop_{DCR2} \text{ (Distribution of Control is shifted to the right of DCR)}$$

Where $Pop_{Control2}$ is the population distribution for the number of contrast enhanced cine angiographic X-ray runs (angiograms) acquired per PCI for the Control group, and Pop_{DCR2} is the population distribution for the number of contrast enhanced cine angiographic X-ray runs (angiograms) acquired per PCI for the DCR group.

Document ID:	<As applicable, per local requirements>	Document title:		Classification:	For internal use
		Statistical Analysis Plan			
Modified:	11MAY2023			Author:	
Version:	3.0	Template ID:	ClinicalStudyTemplate0025	Approver:	
Status:	Final	Template Version Date:	02MAR2018	Page:	30 of 52

Statistical Analysis Plan

Analysis

Descriptive summaries of the total number of contrast enhanced cine angiographic X-ray runs (angiograms) will be presented by treatment group for the FAP and the PP population and will include the number of subjects with non-missing data (n), frequency distributions, median, interquartile range (IQR) and minimum and maximum values.

The number of angiographic X-ray runs is discrete and is likely to be not normally distributed, so the endpoint will be evaluated using a one-sided Wilcoxon-Mann-Whitney test. The results of the Wilcoxon-Mann-Whitney will be displayed as the rank sum and the (one-sided) p-value for the between treatment group difference. When the p-value is lower than the significance level of 2.5% (alpha) we will reject the null hypothesis.

All subjects in the full analysis population will be included in this analysis. The secondary analysis will be repeated for the PP population.

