8.14 Adjustment for Covariates

Analyses to determine whether there is an effect based on e.g. intervention difficulty (as measured by the SYNTAX score), lesion characteristics, patient demographics, physician experience, center etc. will be performed. If an effect on the primary or secondary endpoint is found, applying adjustment analysis will be considered. As a sensitivity analysis, we will then perform an analysis

Document ID:	<As applicable, per local requirements>	Document title:		Classification:	For internal use
Modified:	11MAY2023	Statistical Analysis Plan		Author:	
Version:	3.0	Template ID:	ClinicalStudyTemplate0025	Approver:	
Status:	Final	Template Version Date:	02MAR2018	Page:	38 of 52

Statistical Analysis Plan

of covariance (ANCOVA) for the primary and/or the secondary endpoint adjusting for covariates which are deemed important. The results of the ANCOVA will be displayed through Least-Squares Means (LSMEANS) estimates of the between treatment group difference (with 95% confidence intervals) and the p-value for the between treatment group difference adjusted for covariates.

To investigate whether there is a center effect on the primary outcome, we will calculate the Intra Class Correlation coefficient (ICC) of the total iodinated contrast volume between centers. The ICC is the ratio of the variability between centers to the total variance. The ICC measures to what extent the proportion of the total variability of the primary outcome is accounted for by the clustering of patients within centers. If the ICC is higher than 0.10 we will perform a random effects model on the primary outcome with center as a random effect and treatment as a fixed effect. We will also check the distribution of baseline characteristics between centers. If the centers differ in characteristics, which may influence the primary outcome, such as intervention difficulty, lesion characteristics, patient demographics, physician experience etc, we will perform a random effects model on the primary outcome with center as a random effect and treatment and other covariates as fixed effects (ANCOVA) as a sensitivity analysis. The results of the ANCOVA will be displayed through Least-Squares Means (LSMEANS) estimates of the between treatment group difference (with 95% confidence intervals) and the p-value for the between treatment group difference adjusted for covariates.

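### The primary and secondary tests leave out the factors used to stratify randomisation; to the extent those factors are prognostic, both tests are conservative and the primary confidence interval is wider than it need be

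*SAP*

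**What the plan says.** **Design.** Protocol 6.1 (and the Summary) states: "In the randomization process all subjects within each type of PCI (ad hoc or elective) will be stratified according to the number of vessels". SAP 4.4.2 adds site: "we stratified the randomization by site and within site by type of PCI (ad hoc or elective) and the number of vessels", with permuted blocks of 4 and 1:1 allocation. SAP 9.2 lists changes from the protocol, but not this difference.

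**Analysis.** SAP 8.11.1: "The primary endpoint will be evaluated using a one-sided two-sample t-test". The reported treatment difference and its 95% interval come from that test. SAP 8.11.2: "the endpoint will be evaluated using a one-sided Wilcoxon-Mann-Whitney test". Neither test uses a stratification factor. Protocol 7.6 and 7.7 plan the same unadjusted tests.

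**Provisions for adjustment.** All are conditional:
- SAP 4.5: "If an effect is found applying adjustment analysis, i.e. analysis of covariance adjusting for relevant confounders will be considered as a sensitivity analysis".
- SAP 8.4, after baseline significance tests: "When the groups are not comparable regarding baseline characteristics, adjustment for covariates will be applied as a sensitivity analysis".
- SAP 8.14, if an effect is found: an ANCOVA "adjusting for covariates which are deemed important", as a sensitivity analysis.
- SAP 8.14, for centre: "If the ICC is higher than 0.10 we will perform a random effects model on the primary outcome", with centre as a random effect. A further random-effects model, labelled a sensitivity analysis, follows if centres differ in characteristics.

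The covariates named are SYNTAX score, lesion characteristics, demographics, physician experience and centre. PCI type and planned number of vessels are not named. The analysis by 1, 2 and 3 or more vessels (SAP 8.11.3.2, 8.13) is an exploratory subgroup analysis, not an adjustment.

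**The concern.** Stratified randomisation makes the arms nearly equal on the stratification factors. If a factor predicts contrast volume, the true variance of the difference in means falls accordingly. An unadjusted t-test or rank test still estimates its error from the total variance, so its rejection rate under the null falls below nominal and its interval is too wide.

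There is reason to expect some prognostic value. The procedure steps, angiography included, are repeated for each further vessel (protocol 6.5), and SAP 4.5 itself cites site differences and user preferences as a risk to the contrast comparison. The documents give less reason to expect an effect of PCI type.

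The stake is the precision of the estimated contrast saving, not the validity of the test. In addition, data-driven triggers decide whether design factors are modelled at all, and SAP 8.14 does not say whether the model triggered by the ICC replaces the t-test or sits beside it.

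**Working it through.** **Inputs from the documents.** Means 152.1 and 129.3 ml (difference 22.8), SD 73.0, one-sided alpha 0.025, 80% power, 10% dropout (protocol 7.1, SAP 8.1.1); 177 evaluable per arm, 394 in total (protocol 7.1.1, SAP 8.1.2). The share of variance explained by the factors, R², is not given; it is assumed over 2% to 30%.

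**Step 1: the plan's own figure.** d = 22.8/73.0 = 0.3123. Exact noncentral t power is 79.8% at 161 per arm and 80.0% at 162, so 162 is reproduced; 162/0.9 = 180 and 177/0.9 = 197 follow. At 177 per arm with R² = 0, power is 83.4%.

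**Step 2: closed form at 177 per arm, balanced strata.**
- Unadjusted half-width = t(0.975, 352) × 73.0 × √(2/177) = 15.26 ml.
- Adjusted half-width = 15.26 × √(1−R²). Excess width = 1/√(1−R²) − 1.
- Unadjusted power = 1 − Φ[(t_crit − d√(n/2))/√(1−R²)], with d√(n/2) = 0.3123 × √88.5 = 2.938.
- Adjusted power: noncentral t with d/√(1−R²).

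| R² | Adjusted half-width (ml) | Unadjusted CI too wide by | Power unadjusted | Power adjusted |
|---|---|---|---|---|
| 2% | 15.11 | 1.0% | 83.7% | 84.1% |
| 5% | 14.87 | 2.6% | 84.1% | 85.2% |
| 10% | 14.48 | 5.4% | 84.7% | 87.0% |
| 20% | 13.65 | 11.8% | 86.1% | 90.6% |
| 30% | 12.77 | 19.5% | 87.7% | 93.8% |

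**Step 3: simulation of the primary endpoint.** 394 randomised in blocks of 4, 10% removed at random, 6,000 trials per setting under 22.8 ml and 6,000 under the null. Assumed: 8 sites, PCI type 50/50 with no effect, vessels 75/20/5%, and (ml per extra vessel, site ICC) = (20, 0), (20, 0.03), (30, 0.05), (40, 0.10), (59, 0.10). The variance of the number of extra vessels is 0.31, so R² = ml² × 0.31/73² + ICC.

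Power (%), as plain t-test / t-test replaced by the centre model when ICC > 0.10 / model with all design factors:

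| R² | Site a stratum (SAP) | Site not a stratum (protocol) |
|---|---|---|
| 2.3% | 83.8 / 83.8 / 84.2 | 84.8 / 84.8 / 85.1 |
| 5.3% | 83.5 / 83.5 / 85.0 | 84.0 / 84.0 / 85.4 |
| 10.2% | 84.5 / 84.7 / 87.0 | 83.7 / 83.9 / 86.7 |
| 19.3% | 85.3 / 86.8 / 90.1 | 85.0 / 86.5 / 90.1 |
| 30.2% | 87.1 / 88.2 / 94.1 | 85.4 / 87.1 / 93.2 |

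One-sided type I error (%), unadjusted / adjusted, nominal 2.5, Monte Carlo SE about 0.2:
- Site a stratum: 2.4/2.5, 2.7/2.8, 2.1/2.3, 1.5/2.1, 1.5/2.7.
- Site not a stratum: 2.6/2.8, 2.2/2.4, 2.2/2.4, 1.9/2.1, 1.9/2.7.

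The ICC rule fires in about 0, 1–2, 8–9, 42 and 42% of trials. At a true ICC of 0.10 it is roughly a coin toss.

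A second simulation, with 5 and 10 sites and site a stratum, agrees. At R² = 30% the t-test rejects under the null in 1.1–1.5% of trials, the Wilcoxon test in 1.3–1.4%, and an ANCOVA with the design factors in 2.4–2.6%.

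**Step 4: secondary endpoint, illustrative.** Negative binomial counts with the pilot control mean 46.2 and SD 22.4. At the pilot effect (34.6 against 46.2), both the Wilcoxon test and rank ANCOVA have over 99% power. At an assumed 15% reduction, power (Wilcoxon / rank ANCOVA) is 85.3/85.7, 85.5/85.9, 86.4/88.1, 88.2/92.1 and 91.1/95.5% at R² of about 2, 5, 10, 20 and 33%.

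**The case against.** The strongest reply is that an unadjusted test after stratified randomisation is valid and, if anything, conservative. Power at 177 per arm is at least 83.4% against a planned 80%, and 73.0 is a total SD, so nothing promised is lost. The size of any gain rests on an R² that the documents do not supply. At 5% or less the gain is about 1.5 points or less, and conservatism cannot be told from simulation error. For the secondary endpoint there is no loss at the pilot effect. All of this stands, and it makes the point one of efficiency.

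Second, SAP 4.5 describes adjustment as a sensitivity analysis, so the triggers may never touch the primary inference. That is a fair reading, but the ICC sentence in 8.14 lacks the label, and PCI type and planned vessels are missing on any reading.

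Third, SAP Tables 29/30 list a log-transformed primary analysis. The ml figures then do not apply directly; the percentages carry over only with an R² on the log scale, which is also unknown.

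Fourth, the full analysis population drops subjects with OCT or atherectomy or with neither endpoint available, so balance in the analysed set is approximate. The main simulation removes subjects purely at random.

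Finally, the protocol's site-effect analysis was added after regulatory feedback (revision 02), and replacing a primary test late in an unblinded trial has a credibility cost. The fix has to allow for both.

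**Conclusion.** The concern holds. The two main tests ignore the factors that the randomisation balances, and no provision in the SAP names PCI type or planned vessels as covariates. There is no inflation of type I error, no bias and no threat to the planned power.

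The primary interval is about 1–3% too wide if the factors explain 2–5% of the variance, and about 5–20% too wide at 10–30%. In the simulations, the power gain from adjustment is about 1.5 points or less in the lower range. In the upper range it is about 2–8 points over the plain t-test, or about 2–6 if the ICC rule is credited. These figures depend on the assumed R², vessel mix, number of sites and ICCs.

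The site component of the conservatism applies only if site was a stratum. If it was not, modelling site still reduces residual variance, but leaving it out does not make the t-test conservative. The change is worth making because it is cheap and removes the data-driven choice; the trial is not unsound without it.

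**What to change.** If outcomes by arm have not been seen:
- **Primary:** prespecify one linear mixed model on the scale chosen under SAP 8.11.1, with fixed effects for treatment, PCI type and planned vessels as randomised (1, 2, 3+), site as a random effect (REML), one-sided 0.025. Report the effect with its 95% CI, as a ratio if log-transformed and otherwise in ml.
- **Secondary:** prespecify rank ANCOVA with the same factors.
- Keep the t-test and Wilcoxon test as supportive analyses. Keep the ICC and site analysis as a description of poolability that does not decide whether design factors are modelled.

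If outcomes by arm have been seen, keep the planned tests as primary and report the two adjusted models as named supportive analyses.

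In either case, reconcile protocol 6.1 and SAP 4.4.2 on whether site is a stratum, and record the changes in SAP 9.2.

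**Cost.** A documented departure from the t-test in protocol 7.6 and the conditional site adjustment in 7.3, plus a few lines of code. The factors are held in the randomisation system and tabulated by arm in SAP Table 3, and SAP 9.2 already records one departure from that t-test. SAP 3.0 is dated May 2023 and the documents do not say whether outcomes by arm had been seen, so that status should be stated alongside the change.
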